## **9 PROGRAMMING SPECIFICATIONS**

The rules for programming derivations and dataset specifications are provided in separate documents.

## **10 STATISTICAL SOFTWARE**

All statistical analyses will be performed using Statistical Analysis System (SAS) version 9.4 or later.

## **11 MOCK TABLES, LISTINGS, AND GRAPHS**

The study TLG shells will be provided in a separate document, which will show the content and format of all tables, listings, and graphs in detail.

## 13 APPENDICES

### 13.1 General Rules Deriving Best Overall Response

The BOR is determined once all the data for the subject is known. For this study, a confirmation of complete responses or partial responses is required  $\geq 4$  weeks after the initial assessment of response. In order for SD to be considered the BOR, it must occur  $\geq 7$  weeks following the first dose of study drug. For subjects who do not have a target lesion at baseline, a timepoint response of Non-CR/Non-PD will be treated as SD in BOR derivation, and will be included in DCR and CBR calculation.

To program the BOR per RECIST, the rules below will be followed:

1. The tumor response data collected via the CRFs will be used
2. Any further response assessments after the first PD identified will not be considered for the BOR determination, however they will be presented in the data listings
3. Any tumor assessments after the subject starts a new anti-cancer therapy will not be considered
4. If there are 2 or more consecutive missing adequate tumor assessments, all subsequent assessments will not be considered for the determination of BOR.

Note that the duration between 2 adequate tumor assessments, as well as the duration between the last adequate tumor assessment and death or PD, will be used to identify the cases where 2 or more consecutive tumor assessments are missing. Using the start day and the end day to denote the study days of the two endpoints of the duration, duration = end day – start day. If the duration is longer than  $16\text{ weeks} + 2 \times 7\text{ days}$  (tumor assessment window) – 1 day (ie, 125 days), then it is considered that 2 or more consecutive adequate tumor assessments are missing.

**Table 6 General Rules Deriving BOR per RECIST 1.1**

Timepoint 1 Overall Response	Timepoint 2 $(\geq 4\text{ weeks sinceTimepoint 1})$ Overall Response	BOR b
CR	CR	CR
CR	PR	SD, PD or PR  If a CR is truly met at first time point, then any disease seen at a subsequent time point, even disease meeting PR criteria relative to baseline, makes the disease PD at that point (since disease must have reappeared after CR). Best response would depend on whether minimum duration for SD was met. However, sometimes 'CR' may be claimed when subsequent scans suggest small lesions were likely still present and in

		fact the subject had PR, not CR at the first time point. Under these circumstances, the original CR should be changed to PR and the best response is PR.
CR	SD/PD	SD if duration of SD $\geq$ 7 weeks, otherwise PD
CR	NE	SD if duration of SD $\geq$ 7 weeks, otherwise NE. In a special case, if CR is at the next timepoint after NE, BOR will be CR.
CR a		SD if duration of SD $\geq$ 7 weeks, otherwise NE
PR	CR/PR	PR
PR	SD/PD	SD if duration of SD $\geq$ 7 weeks, otherwise PD
PR	NE	SD if duration of SD $\geq$ 7 weeks, otherwise NE. In a special case, if PR or CR is at the next timepoint after NE, BOR will be PR.
PR a		SD if duration of SD $\geq$ 7 weeks, otherwise NE
SD	Any response	SD if duration of SD $\geq$ 7 weeks, otherwise PD
PD		PD
NE		NE if the subject did not have a post-baseline tumor assessment, or if the subject only had one post-baseline tumor assessment of an early SD (duration < 7 weeks) as the overall response, or post-baseline tumor assessments are not evaluable (ie, recorded as 'NE' as overall responses via the CRF)
UNK		UNK if the subject did not have a baseline tumor assessment

BOR = best overall response, CR = complete response, CRF = case report form, NE = not evaluable, PD = disease progression, PR = partial response, RECIST = Response Evaluation Criteria in Solid Tumors, SD = stable disease, UNK = unknown.

a: If this was the only tumor response assessment (eg study treatment was discontinued).

b: For subjects who does not have target lesion at baseline, a timepoint response of Non-CR/Non-PD will be treated as SD in BOR derivation.

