### 5.1.4 Phase 2 Primary Endpoint

The primary study endpoint for Phase 2 is ORR, defined as the proportion of subjects achieving a BOR of confirmed PR + CR.

Response will be determined by the investigator assessment according to Response Evaluation Criteria in Solid Tumors (RECIST) 1.1 ([Protocol Appendix F](#)). Detailed rules for deriving BOR are provided in [Appendix 13.1](#). Note that BOR of SD has to be achieved at least  $\geq 7$  weeks after the first dose. All response of CR and PR must be confirmed by repeated scans  $\geq 4$  weeks following the initial achievement of response.

Additional efficacy endpoints (determined by investigator assessment):

- Duration of response (DOR), defined as the time from the date of first documented and confirmed CR/PR until the first documentation of disease progression as determined by the investigator or death, whichever comes first.
- Disease control rate (DCR), defined the proportion of subjects achieving a best overall response of CR, PR, or SD. Note that Non-CR/non-disease progression (PD) will be included for subjects without measurable lesion at baseline ([Appendix 13.1](#)).
- Progression-free survival (PFS), defined as the time from first dose date to the date of the first documentation of disease progression as determined by the investigator or death (whichever occurs first).
- Overall survival (OS), defined as the time from first dose date to the date of death (event) or date last known alive or data cutoff date, whichever comes first (censored).
- Clinical benefit rate (CBR): defined as the proportion of subjects with BOR of CR, PR, or durable SD (duration of SD  $\geq 23$  weeks). For subjects whose BOR is SD, duration of SD is defined as the time from the date of first dose to the date of the first documentation of disease progression or death, whichever occurs first. Note that for subjects without measurable lesion at baseline, timepoint response of Non-CR/non-PD will be considered as SD for analysis purpose ([Appendix 13.1](#)).

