## 5.4 Efficacy Analyses

Tumors are evaluated every two cycles (8 weeks) by investigator's assessment based on RECIST 1.1. Assessments will continue until disease progression or initiation of new anti-cancer therapy. Detailed BOR derivation rule is included in [Appendix 13.1](#). Detailed PFS censoring is included in [Appendix 13.2](#).

[figure not shown]
All efficacy parameters will be summarized for the either RES or FAS, or both.

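### The 7-week minimum for stable disease is tested on the date of the SD in the SAP text but on duration of SD in Table 6, and the two tests can give different BOR and DCR

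*SAP*

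**What the plan says.** The text states the minimum twice as a condition on when SD happens. SAP Section 5.1.4: "Note that BOR of SD has to be achieved at least" 7 weeks after first dose. SAP Section 13.1: "In order for SD to be considered the BOR, it must occur" 7 weeks or more after first dose.

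Table 6 in Section 13.1 uses a different quantity. The rows for CR or PR followed by SD or PD, and for SD followed by any response, read "SD if duration of SD $\geq$ 7 weeks, otherwise PD". The rows for CR or PR followed by NE, and the footnote-a rows for a CR or PR that was the only assessment, apply the same duration test but fall back to NE. The NE row covers a subject "if the subject only had one post-baseline tumor assessment of an early SD (duration < 7 weeks) as the overall response".

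Duration of SD is defined once, in the CBR bullet of Section 5.1.4, and only for those already given that BOR: "duration of SD is defined as the time from the date of first dose to the date of the first documentation of disease progression". Death ends the period instead when it comes earlier.

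DCR is the proportion "achieving a best overall response of CR, PR, or SD". It is named in the Phase 2 primary objective (Section 3.1.4) and reported with a Clopper-Pearson interval (Section 5.4.2). On scan timing, Section 5.4 says: "Tumors are evaluated every two cycles (8 weeks) by investigator's assessment based on RECIST 1.1".

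**The concern.** The text asks whether the subject was seen to be free of progression at 7 weeks or later. Table 6, with the only definition available, asks whether progression or death came at 7 weeks or later. A subject whose only non-PD scan was early can fail the first test and pass the second, because the progression or death itself supplies the qualifying time. Such a subject would count as disease control under Table 6 and not under the text.

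The SAP does not say which test governs, so the choice falls to whoever programs BOR. DCR would depend on that choice.

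**Working it through.** **Inputs.** 7 weeks = 7 × 7 = 49 days. First dose is Study Day 1 (Section 8). A duration is end day minus start day (Section 13.1). Table 6 requires Timepoint 2 to be at least 4 weeks (28 days) after Timepoint 1. Scans are every 8 weeks (Section 5.4).

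**The plan's own figure.** Section 13.1 gives the missed-assessment limit as 16 weeks plus two 7-day windows less 1 day: 16 × 7 + 2 × 7 − 1 = 125 days, which reproduces. With a 7-day window the first scheduled scan falls no earlier than 8 × 7 − 7 = 49 days, so the 7-week minimum matches the earliest on-schedule scan.

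**The two tests.** Let *s* be days from first dose to the last non-PD assessment, and *e* days from first dose to PD or death.

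- Text: SD if *s* ≥ 49. For an unconfirmed CR or PR that defaults to SD, I apply this to the date of that assessment.
- Table 6 with the Section 5.1.4 definition: SD if *e* ≥ 49.

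Since *s* ≤ *e*, passing the text test implies passing the Table 6 test whenever *e* exists. The tests split exactly when *s* < 49 ≤ *e*, and then Table 6 is always the more lenient.

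**Cases.**

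| Course | *s* | *e* | Text | Table 6 with Section 5.1.4 definition |
|---|---|---|---|---|
| SD or PR day 28, PD day 57 | 27 | 56 | PD | SD |
| Lone PR day 30, death day 80 | 29 | 79 | NE | SD (PR footnote-a row) |
| SD at 42 days, PD at 46 days | 42 | 46 | PD | PD |
| SD at 56 days, PD at 84 days | 56 | 84 | SD | SD |
| Lone PR at 56 days, no PD or death | 56 | none | SD | cannot be computed |

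In the first case the assessments are 57 − 28 = 29 days apart, so the 4-week column of Table 6 is met. In the last case the definition gives no end date, although the footnote-a rows are written for subjects with a single assessment.

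**Circularity.** The definition applies to subjects whose BOR is SD, while Table 6 would use it to decide whether BOR is SD.

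**Size.** Each subject who switches moves DCR by 1/N. With assumed denominators, that is 1/50 = 2.0 points or 1/100 = 1.0 point.

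**The case against.** The best defence is that the text controls. It states the timing condition twice, once directly ahead of Table 6, and the table is headed as general rules, so its wording can be taken as shorthand. The definition of duration sits in the CBR bullet and is limited to subjects already classed as SD, so it may never have been meant for Table 6. The footnote-a rows support this: for a subject still alive without progression they work only if time is measured to the assessment.

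This shows what was probably intended. It does not remove the problem, because Table 6 uses a term that the SAP defines in one place only, and that definition gives another answer. The limited scope of the definition is itself a reason to give Table 6 its own test.

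Three narrower points stand:

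- The 4-week column limits the two-timepoint examples. SD on day 30 with PD on day 57 is 57 − 30 = 27 days apart and does not literally fit the row.
- A reader might infer that a lone early SD followed by death after week 7 counts as disease control. The documents do not establish that. The word *early* in the NE row can be read as describing the time to the scan, which gives NE and agrees with the text. That case is ambiguous; the lone early PR is not covered by the NE row and does split the rules.
- Scans before week 7 are off schedule, so few subjects can be affected.

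**Conclusion.** The SAP gives two tests for one minimum and does not rank them. Where both can be computed they differ only when the last non-PD scan is under 49 days from first dose and PD or death is at 49 days or later, and the difference always raises DCR under Table 6. Where there is no PD or death, the Table 6 test is undefined.

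The effect is likely small. An affected subject needs an off-schedule early scan, no later non-PD scan, and PD or death at 49 days or later. The SAP gives no frequency for this, so no overall bias in DCR can be stated beyond 1/N per subject. A reader might infer that the 7-week minimum has no force at all under Table 6. That goes too far: PD at 46 days after SD at 42 days is still PD under both tests.

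ORR, the Phase 2 primary endpoint, is unaffected because it counts only confirmed CR and PR. CBR is unaffected in the worked examples, since 56 and 79 days are both below 23 × 7 = 161 days.

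The conclusion rests on applying the Section 5.1.4 definition to Table 6, for which the SAP offers no alternative.

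**What to change.** - In every Table 6 row that defaults to SD, replace the duration test with: *at least one assessment of SD or better (or Non-CR/Non-PD) ≥ 49 days after first dose*.
- In the NE row, replace the early-SD wording with: *SD assessed < 49 days after first dose*.
- State that duration of SD, as defined in Section 5.1.4, is used for CBR only.

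With these changes, SD or PR on day 28 followed by PD on day 57 is PD, a lone PR or SD on day 30 is NE whatever follows, and a lone PR at 56 days without an event is SD. Table 6 then agrees with the text. The cost is SAP wording and one line of the BOR derivation; no new data are needed. DCR may come out slightly lower than under the Table 6 wording.

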## 13.2 PFS Censoring Rules

For the main analysis of PFS, the censoring rules in this SAP and definition of progression date follow the principles of the FDA “Guidance for Industry Clinical Trial Endpoints for the Approval of Cancer Drugs and Biologics (2018)”. Table 7 below shows the censoring rules for the derivation of PFS.

**Table 7 Censoring Rules for the Derivation of PFS in Primary Analysis**

No.	Situation	Date of Event (Progression/Death) or Censoring	Outcome
1	No baseline or post-baseline tumor assessments	Date of first dose	Censored
2	Progression documented between scheduled visits	Date of first radiologic PD assessment	Event
3	No progression at the time of data cutoff	Date of last adequate radiologic assessment prior to or on date of data cutoff	Censored
4	New anticancer treatment started	Date of last adequate radiologic assessment prior to or on date of new anticancer treatment	Censored
5	Death before first PD assessment	Date of death	Event
6	Death between adequate assessment visits a	Date of death	Event
7	Death or progression after more than one missed visit/tumor assessment b	Date of last adequate radiologic assessment before missed tumor assessments	Censored

CR = complete response, PD = disease progression, PFS = progression-free survival, PR = partial response, SD = stable disease.

a Adequate tumor assessment is radiological assessment of CR, PR, SD, non-CR/non-PD or PD as determined by investigators at regular interval as defined in the protocol. Any tumor assessments after new anticancer treatment starts will be removed in the definition of PFS.

b Defined in [Appendix 13.1](#).

The priority of the censoring rules is as follows:

1. If the subject had PD or death, the following sequence will be applied:
  - If a subject did not have a baseline tumor assessment (No. 1), the subject will be censored on the date of first dose. If the subject died within 125 days following first dose and did not receive a new anticancer treatment, it will be counted as an event at the date of death. If a subject had new anticancer treatment before PD or death (No. 4), the subject will be censored on the date of the last adequate tumor assessment prior to or on the date of new anticancer treatment.

- If a subject missed two or more tumor assessments (>125 days) before PD or death (No. 7), the subject will be censored on the date of the last adequate tumor assessment before PD or death. Note that if a subject is censored by both this criterion and the anticancer treatment criterion, the earliest censoring date will be used.
- Otherwise, if a subject had an event (No. 2, No. 5, or No. 6), the earliest event date will be used.

2. If a subject did not have PD or death, the censoring date will be the earliest censoring date if the subject met multiple censoring criteria (No. 1, No. 3, No. 4 or No. 7). Supportive analyses will be provided to evaluate robustness of the main analysis:

- Among FAS subjects who started on 450 mg, if more than 15% of subjects are censored due to COVID-19, then a sensitivity analysis will be performed, allowing subjects to have events after COVID-19 related censoring: events or valid assessment after  $\geq 2$  consecutive missing assessments (at least 1 due to COVID-19) will be included in PFS derivation, whereas these events and assessment would have been excluded in the main PFS analysis using the FDA censoring rule.
- Among FAS subjects who started on 450 mg, if more than 15% of subjects are censored due to initiation of new anti-cancer therapy, then a sensitivity analysis will be performed: these subjects will be assumed to have events occurred at the censoring date, whereas these subjects will be censored at the censoring date in the main PFS analysis.
- Among FAS subjects who started on 450 mg, if more than 15% of subjects are censored in the main PFS analysis AND discontinued treatment due to clinical disease progression, then a sensitivity analysis will be performed: discontinuation due to clinical disease progression will be considered as a valid assessment of radiological PD, and the FDA censoring rule will be applied to determine the event/censoring status and date.

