**Table 2 List of PFS analyses**

Purpose	Analysis set	Presentation grouping [Table, Figure]
Protocol defined	FAS	Treatment groups [TF]
Protocol defined subgroup	FAS CCI [REDACTED]	ESR1 status (Mutant, Wild type) [T]
CCI [REDACTED]	[REDACTED]	[REDACTED]
[REDACTED]	[REDACTED]	[REDACTED]
[REDACTED]	[REDACTED]	[REDACTED]
[REDACTED]	[REDACTED]	[REDACTED]
[REDACTED]	[REDACTED]	[REDACTED]
Sensitivity analysis is not included in the table and will be detailed in TLG shells.		
ESR1 = estrogen receptor, F = figure, FAS = Full Analysis Set, G = graph, PFS = progression-free survival, PgR = progesterone receptor, T = table.		

For DOR, the analysis will include subjects with confirmed responses. The same logics in censoring rules as those for primary analysis of PFS will be applied. If there are  $\geq 7$  subjects with confirmed responses, the median of DOR will be estimated using Kaplan-Meier methodology; median DOR and the corresponding 2-sided 95% CI will be presented by treatment groups on RES. If there are  $< 7$  subjects with confirmed responses, DOR will be listed.

For OS, the distribution of OS will be estimated using Kaplan-Meier methodology. Median survival time and the corresponding 95% CI, survival rates at 6, 12, 18, 24, 30 and 36 months, and corresponding 95% CIs will be estimated using Kaplan-Meier method. The analysis will be presented by treatment groups, *ESR1* mutation groups, and PgR status.

In addition, waterfall plot of best percentage change may be provided for RES subjects started on the 450 mg dose and color-coded by *ESR1* mutation groups.

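### The SAP gives two PFS censoring dates after missed scans (Table 7 No. 7) and applies No. 7 to subjects its own row excludes, so the date can depend on later outcome

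*SAP*

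**What the plan says.** Three parts of SAP Appendix 13.2 deal with censoring for missed assessments (No. 7).

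- **Table 7, row 7.** The situation is "Death or progression after more than one missed visit/tumor assessment" and the date is the "Date of last adequate radiologic assessment before missed tumor assessments". Footnote b takes the definition of the gap from Appendix 13.1.
- **Priority list, item 1 (subjects with PD or death).** The bullet that cites No. 7 says "the subject will be censored on the date of the last adequate tumor assessment before PD or death".
- **Priority list, item 2 (subjects without PD or death).** It says "the censoring date will be the earliest censoring date if the subject met multiple censoring criteria (No. 1, No. 3, No. 4 or No. 7").

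Three other places bear on the reading.

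- Appendix 13.1 identifies a gap from "the duration between 2 adequate tumor assessments, as well as the duration between the last adequate tumor assessment and death or PD", with a threshold of more than 125 days. Its rule 4 for best overall response disregards all assessments after such a gap.
- The COVID-19 supportive analysis in Appendix 13.2 would bring back events and valid assessments after a gap, "whereas these events and assessment would have been excluded in the main PFS analysis using the FDA censoring rule".
- Section 5.4.2 says of DOR: "The same logics in censoring rules as those for primary analysis of PFS will be applied".

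**The concern.** One numbered rule has two dates, and the SAP does not say which prevails. The priority list also uses the rule for subjects who cannot meet it as row 7 is worded.

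The dates differ only for a subject who misses two or more scans, returns to adequate scanning, and later progresses or dies. Two programmers working from the same SAP could then censor that subject on different sides of the gap. For a subject who returns to scanning and does not progress, they could also disagree on whether No. 7 applies at all.

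At stake is the independence of censoring from outcome that Kaplan-Meier estimation needs. No. 7 turns any event after the gap into a censoring. Follow-up kept after the gap is therefore event-free by construction, and keeping it for some subjects and not others, according to what happened later, distorts the curve. The planned PFS rates at 3, 6, 9 and 12 months and the medians of PFS and DOR all rest on these dates.

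**Working it through.** **Inputs.** Scans are every 8 weeks, or 56 days (Section 5.4). The gap rule and the No. 7 wordings are from Appendices 13.1 and 13.2. The scan histories are constructed for illustration and are not trial data.

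**Threshold.** 16 × 7 + 2 × 7 − 1 = 125 days, which reproduces the SAP's figure.

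**History A, gap running up to the event:** SD day 56, PD day 224. The gap is 224 − 56 = 168 days, above 125. Row 7 gives day 56 and the item 1 bullet gives day 56, so there is no conflict.

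**History B, scanning resumes, then PD:** SD day 56, scans at days 112 and 168 missed, SD day 224, PD day 280. The gap is again 168 days. It lies between two adequate assessments, which Appendix 13.1 counts.
- Row 7: day 56.
- Item 1 bullet: day 224.
- Difference: 224 − 56 = 168 days.

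**History C, identical to B up to day 224, then SD at day 280 and no PD or death.**
- Item 2 with No. 7 at row 7's date: min(56, 280) = day 56.
- Row 7's situation enforced, so that only No. 3 applies: day 280.
- Difference: 280 − 56 = 224 days.

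**Combining the readings.**

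| Reading | B (later PD) | C (no PD) |
|---|---|---|
| Priority list followed (bullet's date; No. 7 in item 2) | 224 | 56 |
| Table 7 alone (row 7's date; row 7's situation enforced) | 56 | 280 |
| Bullet's date; row 7's situation enforced | 224 | 280 |
| Row 7's date for everyone with a gap | 56 | 56 |

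Only the last row gives the same date whatever happens later. It is also the only row in which nothing after the gap is used, as the COVID-19 text says of the main analysis.

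**In months.** Using the SAP's divisor of 30.4375 (Section 5.6.1), days 56, 224 and 280 are about 1.8, 7.4 and 9.2 months. The choice decides whether such a subject is in the risk set at 3 and 6 months, and under one reading at 9 months.

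**DOR.** Take PR day 56, confirmed day 112, scans at days 168 and 224 missed, PR day 280, PD day 336. The gap is 280 − 112 = 168 days, above 125.
- Row 7: censored at day 112, so DOR is 112 − 56 = 56 days.
- Item 1 bullet: censored at day 280, so DOR is 280 − 56 = 224 days.
- Difference: 168 days.

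**The case against.** The strongest reply is that the intended date can be found in the SAP. Table 7 is presented as the set of censoring rules and the list only as their order of priority, so the bullet can be read as shorthand for row 7. The COVID-19 text and rule 4 for best overall response point the same way. This supports the pre-gap date, but it also means the bullet as written uses a scan that the SAP says elsewhere is excluded.

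A second reply is that the contrast of day 224 with day 56 mixes readings: it overrides row 7's date for one subject and ignores row 7's situation for the other. Read strictly, a subject without PD cannot meet No. 7, and No. 3 applies. It is fair to say that this contrast belongs to one reading. But Table 7 taken alone gives day 56 with PD and day 280 without, which depends on outcome in the other direction.

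A third reading limits No. 7 to gaps that run directly up to PD or death. History B then becomes an event at day 280. That conflicts with the Appendix 13.1 definition imported by footnote b and with the COVID-19 text, and it leaves No. 7 in item 2 with no one to cover.

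It stands that the case is narrow, that PFS and DOR are additional endpoints with no comparison specified, and that the SAP places programming rules in separate documents, so the dates actually programmed are not known. Those documents do not cure a rule that the SAP itself states in two ways.

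**Conclusion.** The concern holds. Row 7 and the priority list give different dates for No. 7 when scanning resumes after a gap of more than 125 days and PD or death follows, and item 2 uses No. 7 for subjects whom row 7 excludes. Both the priority list as written and Table 7 taken alone make the censoring date depend on later outcome.

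In the illustrations the dates differ by 168 days for PFS with later PD, 224 days for PFS without PD, and 168 days for DOR. These are differences for single constructed subjects. The number of subjects affected and the effect on any median or rate cannot be derived from the SAP. The main PFS analysis and DOR are affected; the primary endpoint, ORR, is not. Whether No. 7 covers subjects without PD can also change the count for the 15% trigger of the COVID-19 sensitivity analysis. The text should be corrected, though it does not threaten the primary result.

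**What to change.** State one date for No. 7 and apply it whatever happens later. Two edits to Appendix 13.2 do this:

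1. In the item 1 bullet that cites No. 7, replace the date with row 7's: the last adequate assessment preceding the missed ones.
2. Widen row 7's situation to any subject with a gap of more than 125 days as defined in Appendix 13.1, with or without later PD or death, so that item 2 refers to a defined case.

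Deleting No. 7 from item 2 would be a shorter edit than the second, but it leaves day 56 with PD and day 280 without, so the dependence on outcome remains. Counting PD after scanning resumes as an event would change the stated rule and belongs, if anywhere, in a supportive analysis.

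The cost is the wording of one bullet and one table row. No new data or analysis is needed.
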